Aim 3: To examine the effect of technology-enhanced TPC for FCGs on healthcare costs. Recognizing the synergy between FCGs and care recipients, we hypothesize that costs from all stakeholders (FCGs, care recipients, and health systems) of providing palliative care to care recipients in the intervention group will decrease compared to usual care. Using the Ambulatory and Home Care Record (AHCRR), which is rooted in the societal perspective,^{1,25} we will measure all costs of care for the FCG and care recipient, irrespective of payer.^{26,27} We hypothesize that there will be a net decrease in costs for 6 months post-enrollment from a societal perspective following

the addition of a TPC for FCG in the intervention group compared to the costs of care for the FCG and care recipient in the usual care group.

This revised application is responsive to **FOA PAR-16-250**: examining an innovative model of TPC for FCGs in underserved rural areas to address the public health imperative based on the rapid growth in the need for palliative care services.²⁸ Our study is designed to extend transitional and palliative care science to contribute to the 2016 strategic plan priority of the National Institute of Nursing Research of exploring novel approaches for effective interventions to provide compassionate support to FCGs of patients with life-limiting illnesses.

RESEARCH STRATEGY

A. SIGNIFICANCE

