Part 2: At home technology-enhanced intervention. A minimum of weekly video visits will occur during Part 2 of the study. The first video visit by the nurse with the FCG will occur within 24-48 hours of hospital discharge. During visits the nurse will: (1) Provide ongoing education, guidance, and support to the FCG to develop self-care and caregiving skills; (2) Coordinate the implementation of the community-based aspects of the transitional care plan to address the FCG's as well as the patient's needs; (3) reaffirm and provide education and anticipatory guidance for the use of individualized FCG Readiness Plans for common care recipient symptoms such as pain, breathlessness, anxiety, etc.; (4) if requested, collaborate through active dialog with the local community resources included in the transition plan; (5) if requested, collaborate with the primary care provider/specialty providers related to goals of care; (6) coach the FCG in preparation for care recipient/provider office visits; and based on her continuing assessments; and (7) provide additional video visits/phone calls to support the FCG. Palliative and transitional care intervention objectives and activities are listed in Figure 2. Frequency type and length of contacts will be documented to quantify the dose effect of the intervention.

Video visits will be accomplished via the Zoom application using the equipment of choice by the FCG: a 3G-enabled iPad (provided by the study) or their own Smartphone or personal computer enabled with a camera for video visits. Any required training on the equipment and software will be conducted by the study coordinator in person or over the phone during Part 1 of the intervention with additional 24/7 technical support provided by the study coordinator and the IT solutions contractor (Caryl Technologies, LLC) during Part 2.

The intervention will continue for the FCGs during the 8-week period. Based on our prior experience with the FCG population, it is possible that the care recipient may be placed in a long-term nursing facility or die during the 8-week study period. In the case of the death of the care recipient, bereavement support (phone calls, video visits, and written educational materials) for the FCG will be provided for the duration of the 8-week intervention interval.

Control group: Usual care condition

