Authentication of key biological and/or chemical resources. Findings regarding sex differences in FCG outcomes ^{9,152} have not been reported, although the majority of FCGs are female.¹⁵³ Based on the unequal sex distributions in other studies of FCGs,¹⁵⁴⁻¹⁵⁶ we anticipate the enrollment of FCG female participants will be greater than males. We have no evidence to suggest that the sex distribution of FCGs will impact our outcomes.

Variables and Their Measurements

Copies of instruments we will use are found in Appendix B, including core data elements for caregiving research suggested by the Palliative Care Research Cooperative Group.¹²⁹

Table 1 summarizes the concepts, variables and measures, and timing of data collection. Data, including sample characteristics (age, sex, race/ethnicity, marital status, education, how long the FCG has been providing care to the care recipient, any computer/Smartphone experience and availability) and questionnaires, will be collected by a study coordinator from all enrolled participants after obtaining consent (baseline) via in-person interviews prior to the care recipients' hospital discharge.

Self-reported data will be obtained by computer-assisted interviews, telephone or mailed questionnaires, based on FCGs preferences, from all FCGs at 2 weeks, at the end of the intervention period (Aims 1 and 2) and at 6 months (Aim 2). If FCGs choose to complete questionnaires independently, they will have the choice of receiving a packet by mail or a link to complete questionnaire electronically via REDCap. If any FCG would like assistance completing the questionnaires, the study coordinator will provide assistance. Given the complexity of cost data, participants will be telephoned monthly for 6 months post-hospital discharge for cost data collection needed to address Aim 3.

If the care recipient dies, we will collect Aims 1 and 2 outcomes data from the FCG approximately 2 weeks later, given that grieving family members' distress and satisfaction with care should be more stable 2 weeks after their loved one's death.^{157,158}

In order to assure the safety of participants, the intervention nurse or study social worker will follow up by phone with all participants, regardless of, who report a score of >10 on depressive symptoms on any questionnaire or if an intervention or control caregiver reports via phone, survey or email information that raises the concern for elder mistreatment or abuse about family or

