Aim 3: Examine the effect of technology-enhanced TPC for FCGs on healthcare costs. The Ambulatory and Home Care Record (AHCR) will be used as our healthcare cost measure. The AHCR is designed to capture costs from a societal perspective, implying that costs from all stakeholders (FCG, care recipients, and health systems) will be collected. Developed for the Canadian health system where healthcare is primarily publicly funded,¹ the AHCR will be modified for our study to collect expenditures paid for by any type of payer (e.g., commercial, government, or other insurance; and self-pay/no insurance) instead of simply publicly-financed expenditures as in the original AHCR. Third party insurance refers to any supplemental insurance over and above the primary insurance that the patient has (see Table 2). Thus, the proposed change to the original AHCR measure is only to increase clarity regarding funders and therefore we do not anticipate any threat to the AHCR's validity. The AHCR captures self-reported utilization and cost information for care provided by all FCGs and other unpaid caregivers, paid care received at home (e.g., home health care) and outside of the home (e.g., doctor/therapy appointments), as well as medications, supplies, and equipment. Out-of-pocket costs refer to all care-related expenses not paid for by the insurance. These data will be collected monthly for 6 months following each care recipient's discharge from the index hospitalization to minimize recall bias and to account for any time lag in billing systems. The FCGs will be prompted to have all bills received during the preceding month available during the monthly AHCR data collection. Agreement between care recipients' reports on the AHCR and administrative data range from moderate ($\kappa=0.41$; 95 percent confidence interval, 0.16–0.61) for physician visits to perfect ($\kappa=1.0$) for physical therapy visits.²⁵

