For analyses of costs, standard descriptive statistics including mean, median, standard deviation, minimum and maximum will be provided for all cost outcomes measured individually and also for the overall cost measure. The difference in overall cost between the intervention and control group will provide an estimate of the cost impact of the TPC for FCG model of care. The difference in hospitalization and ED costs between the treatment and control arms will determine the cost avoidance potential of implementing the intervention. The difference in FCG cost, a component of the overall costs, between intervention and control groups will provide evidence on the impact of the intervention on this specific cost component. Both the descriptive and multivariable-adjusted measures will be estimated for 8 weeks and 6 months. Because the distribution of healthcare costs and length of stay (LOS) are generally skewed, both the LOS and costs will be log-transformed before any estimation; the estimated coefficients can then be interpreted as the approximate percentage changes. Alternatively, we will also explore modeling costs and LOS with a generalized linear model with gamma distribution and log link.¹⁸³ Furthermore, to account for the possibility that some of the study patients will die before the six-month follow-up; we will also apply econometric methods of censored regression.^{184,185}

Data Management

Following the data safety monitoring plan (see Protection of Human Subjects), the PI and investigative team will review the data to ensure quality, adherence to study procedures, and safety at monthly study team meetings. All participant data will be coded and stored in a secure, locked cabinet in the study coordinator's office. All data will be entered into the web-based Research Electronic Data Capture (RED-Cap) database and maintained on secure, password-protected servers, accessible only to members of the study team. The database will be exported to the statistical analysis package, SAS, to be analyzed anonymously, and standard Mayo Clinic policies and safeguards will be used to protect the confidentiality of the subject records.

Expected Outcomes

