schedule data collection will be made approximately 2 weeks and then monthly after hospital discharge at the number and time of day the FCGs suggest. Depending on the participant's preference, they may choose to be contacted by text message or email instead of receiving a phone call. The study coordinator will use a cell phone with caller identification recognizable to the participants to assure completeness of follow-up data. If at first we are unable to connect, phone calls will be made at varying times during the day. Our prior experience related to completion of data collection after hospital discharge indicated that the majority of patients and FCGs do not venture far from home soon after discharge. We will provide remuneration to all FCG participants commensurate with the time spent in the study (intervention activities for intervention group, data collection for both groups) to encourage continued engagement. If a care recipient dies during the data collection period, it may be difficult to collect subsequent data from the FCG. Providing reminder phone calls as an attention control device will augment the continued engagement of control FCGs in the study. Recall of cost components will be enhanced by monthly data collection up to six months after the care recipient's index hospitalization to account for any time lag in billing systems. The FCGs will be provided a checklist and prompted to have all bills received during the preceding month available during the monthly AHCR data collection.

Resource Sharing Plan/Data Sharing Plan

The research will be disseminated at national scientific meetings, and manuscripts will be generated from the Specific Aims. A clean de-identified dataset will be available to qualified investigators through communication with the PI after primary results manuscripts are accepted.

C. Timetable

STUDY TIME LINE	Year 1				Year 2				Year 3				Year 4				Year 5			
	Tasks	Q1	Q2	Q3	Q4	Q1	Q2	Q3												
Study start-up: regulatory & training																				
Subject accrual & data collection																				
Data Analysis																				
Cost Analysis																				
Dissemination & final report																				

D. Future Directions

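### Aim 3 hypothesises societal costs over 6 months from enrollment, but the cost record runs from hospital discharge, with no rule for costs between randomization and discharge

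*Combined protocol and SAP*

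**What the plan says.** The hypothesis in Specific Aims, Aim 3, is a "net decrease in costs for 6 months post-enrollment from a societal perspective". The same paragraph promises that "we will measure all costs of care for the FCG and care recipient, irrespective of payer".

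The collection schedule starts elsewhere. Under Variables and Their Measurements, "participants will be telephoned monthly for 6 months post-hospital discharge for cost data collection needed to address Aim 3". The description of the Aim 3 measure agrees: "These data will be collected monthly for 6 months following each care recipient's discharge from the index hospitalization". Potential Problems & Alternative Strategies describes "monthly data collection up to six months after the care recipient's index hospitalization". Table 1 lists the cost record as monthly for 6 months, with no baseline administration.

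Research Design places randomization after consent. The Experimental Group section places enrollment during the hospital stay. Part 1 (Pre-discharge intervention) has the nurse begin within 24 hours of enrollment and continue until discharge.

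The Analytical Plan reports costs at 8 weeks and 6 months without saying from when. It adds that "both the LOS and costs will be log-transformed before any estimation", without saying which hospital stay LOS covers.

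**The concern.** In every dyad enrolled as planned, an interval that is already randomized, and already treated in the intervention arm, comes before the cost window opens. During it the nurse works on discharge itself. Part 1 and Appendix A list transition planning with acute care staff, arrangements for transport and equipment, and confirmation of readiness on the day of discharge. Such work could lengthen or shorten the remaining stay.

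The clock therefore starts at an event after randomization that the intervention might move. If the arms differ in remaining stay or in deaths before discharge, the cost of that difference is not systematically counted, and the dyads with a cost window may no longer be fully comparable. A conclusion about net societal cost from enrollment would then rest on data that do not cover the period named.

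**Working it through.** No stated figure depends on the time origin, so the main check sets the text side by side.

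**Time origins**
- Hypothesis (Specific Aims, Aim 3): enrollment.
- Randomization (Research Design): after consent, during the index stay.
- Start of intervention (Part 1): within 24 hours of enrollment, before discharge.
- Cost collection (Variables and Their Measurements; Aim 3 measure): discharge. The retention text counts from the index hospitalization.
- Cost analysis (Analytical Plan): 8 weeks and 6 months, no origin given.

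**Routes by which costs before discharge could still enter**
- Bills. Monthly calls ask for bills received in the preceding month, with no date-of-service rule. An index-stay bill that arrives after discharge may be recorded in one dyad and not in another.
- Table 2. It has a hospitalization line that neither includes nor excludes the index stay. The avoided-cost contrast is limited to readmissions and ED visits.
- LOS. It is modelled, but the stay is not named, and nothing says that index-stay days are costed into the total.
- Caregiver time and travel during the stay. No collection point is stated.
- Deaths. Censored regression is planned for deaths before six months. That deals with a window cut short. It does not define one for a recipient who is never discharged.

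**Calendar share missed.** The documents do not give the time from enrollment to discharge. For an assumed d days and a 6-month window of 365.25/2 = 182.6 days, the share is d/182.6:
- d = 1: 0.5%
- d = 3: 1.6%
- d = 7: 3.8%
- d = 14: 7.7%

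The discharge-based window adds the same d days at its end. The share of cost could exceed the share of time because the missed days are inpatient days, but no cost per day is given.

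**A yardstick in dollars.** Sample Size and Power Calculations gives a monthly cost SD of $1,000; the planned size is 100 per group. If that SD applies to each dyad's average monthly cost, the detectable difference at 80% power and two-sided 0.05 is (1.960 + 0.8416) × 1,000 × √(2/100) = 2.8016 × 141.42 = $396 per month. Sustained for 6 months, that is 6 × 396.2 = $2,377. At the 0.01 level of the Analytical Plan, the plan's own effect size of 0.487 gives 0.487 × 1,000 = $487 per month, or 6 × 487 = $2,922. These are derived values, not targets in the plan, and the 6-month totals assume survival to 6 months. An uncounted pre-discharge difference of this order, in the opposite direction, would offset a detectable saving.

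**The case against.** The strongest reply is that this is one phrase in the Aims against consistent operational text, and that discharge is the trial's clock elsewhere: the 8-week intervention and the 2- and 8-week assessments are counted from it. Both arms use the same origin, intent to treat is specified, and no intervention activities are planned for care recipients. This stands as far as it shows that no bias has been demonstrated. It does not reconcile the hypothesis with the collection window, and it gives no rule for costs before discharge.

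Four stronger readings are tempting, and the documents do not support them.
- *Index-stay costs are left out in every dyad.* The text does not say so. Bills can leak in and LOS is undefined. Handling is unspecified and unsystematic.
- *The randomized comparison is broken.* Bias needs the arms to differ in discharge timing or in death before discharge. The documents show that this could happen, not that it does.
- *The omitted days are large against a 20% cost target.* The plan has no such target. Its 20% refers to hospitalizations and ED visits, and its cost assumption is $2,000 per month in both cohorts.
- *Nurse time is missing because of the time origin.* Table 2 has no line for delivering the intervention before or after discharge. Moving the origin would not fill that gap, although the word *net* requires it to be filled.

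**Conclusion.** The conflict in time origin is explicit. As written, the plan cannot deliver the comparison that Aim 3 states: costs between randomization and discharge have no systematic capture, and recipients who die before discharge have no defined window. The effect on the cost difference cannot be computed from the documents, which give neither the length of the interval nor a cost per inpatient day. It matters to the extent that the arms differ before discharge in remaining stay, death or intervention cost, and the plan does not commit to showing whether they do. The gap should be closed before costs are analysed, because the choice determines whether the trial can report net societal cost from enrollment or only cost after discharge.

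**What to change.** Use one time origin in the Aim 3 hypothesis, the collection schedule and the analysis.

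**Preferred: randomization.**
- Add index-stay days and hospital cost from randomization to discharge from the care recipient's health record. Recruitment already describes consent to record data; confirm that it covers billing data.
- Count recipients who die before discharge, with their costs up to death.
- Assign bills by date of service and close the window 6 months after randomization. Calls run to 6 months after discharge, which is later, so no extra calls are needed.
- Cost the nurse contacts both before and after discharge. Part 2 already states that "Frequency type and length of contacts will be documented to quantify the dose effect of the intervention", and Appendix A requires pre-discharge encounters to be documented.
- State that caregiver time and travel during the stay are excluded, or add one item to the first monthly call.
- Say which stay LOS refers to.

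The cost is revised wording, one record extraction per recipient and possibly one question.

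**Alternative: discharge.** Restate Aim 3 as post-discharge costs, drop *net* and *post-enrollment*, and report index-stay days from randomization to discharge by arm as a check. This costs wording and the extraction of days, but gives up the claim about societal cost from enrollment.

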The RCT design will be used to test the efficacy of technology-enhanced TPC for FCGs on outcomes related to the FCGs' experience and determine the impact on costs from a societal perspective. After informed consent is obtained, FCGs will be randomly assigned to one of two groups by computer-generated randomization lists: 1) the experimental group or 2) a "usual care" or control group. Consistent with transitional care models,^{142,143} the intervention period will continue for 8 weeks after care recipients are discharged from the hospital.

Setting

The setting for this study is the Mayo Clinic Hospitals in Rochester and Mankato Minnesota and LaCrosse Wisconsin. While patients at the Mayo Clinic Rochester Hospital come from all regions of the US and many foreign countries, the majority (80%) come from within a 120-mile radius of Rochester. The same holds true for the more community-based hospitals in Mankato and

LaCrosse. Of the 31 counties in the major catchment area of the clinic, 26 are designated as rural or federally designated medically underserved areas.^{144,145}

The Palliative Care consulting service is available to any patient hospitalized at Mayo Clinic Hospital — Rochester, Mayo Clinic Health Systems in Mankato and/or LaCrosse. The Mayo Clinic Rochester service is organized into 3 teams. Each team has a physician and an advanced practice clinician, plus students. On average there are 6-10 new consults per day. The palliative care teams meet daily to discuss new and continuing patients. Dr. [REDACTED] (Co-I), [REDACTED] (pharmacist), [REDACTED] (SW) and [REDACTED], (APN) are members of the palliative care consulting service and members of our research team.

The Palliative Care consulting service in the Mayo Clinic Health System hospitals in Mankato and /or LaCrosse is smaller and includes one team for each site. The research coordinator will work independently of the Palliative care clinic team at these hospitals.

Sample – Target population

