The FCGs randomized to the control group will receive a phone call by a member of the study team reminding them of the study and the next scheduled data collection date. This call will account for the nonspecific conditions of expectancy, social support, and attention considered necessary to generate placebo effects.¹⁵¹ If concerns are identified during the attention control interaction between FCGs and study personnel, the FCGs will be advised to call their primary care provider. Control group care recipients will receive consult visits by the palliative care team while hospitalized, usual hospital discharge planning, and primary and specialty care in the community after hospital discharge. Services received by the FCGs will be collated and considered for analysis as confounding factors. We do not anticipate care recipients will participate in any study activities.

Study procedures

Study Preparation and Monitoring. Following IRB approval, the study coordinators and clinician members of the research team will be educated on the purpose of this study, as well as trained in all study procedures by the investigators; training will occur at study initiation and at subsequent quarterly reviews of study procedures.

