Aims 1 and 2. Statistical analyses of Aims 1 and 2 will be performed in a similar manner. Every FCG will be evaluated using various scales and survey instruments at baseline, 2 weeks, and 8 weeks post patient discharge (Table 1). We will use a response-feature analysis as our primary approach in analyzing these repeated measures data.¹⁸¹ For each FCG, the magnitude of the scores from the respective instruments will be plotted versus time (measured in months); least squares regression will be used to estimate a participant-specific rate of increase in points per month. This slope parameter estimate will be used as the response feature for each participant and is the primary endpoint for this study. The primary analysis of this endpoint will be analyzed using a two-sample t-test or Wilcoxon rank-sum test, as appropriate. The endpoints will also be analyzed using a fixed-effects linear regression model. This model will use the estimated regression-slope response-feature as the dependent variable and have independent variables consisting of intervention (yes, no) as well as any baseline covariates such as FCGs’ age, employment status, etc. These analyses will adjust for any possible imbalances in these baseline covariates among FCGs that occur due to the randomized assignment to the intervention. This analysis approach will hold for those endpoints collected only at two time points (i.e., baseline and 8 weeks).

Aim 3. Descriptive statistics, including mean, median, and standard deviation (minimum and maximum) for the utilization measures (i.e., hospitalizations and ED visits) will be provided. Considering the count nature of the utilizations, and to also account for any potential differences between the baseline characteristics of the care recipients in the two study arms, we will use Poisson regression to model various utilization outcomes.¹⁸² We expect that the gains (decreased healthcare utilization and costs) will be sustained beyond the enrollment period. Therefore, both descriptive and multivariable-adjusted measures will be estimated for the intervention period and the subsequent months post-intervention. A limitation of this economic approach will be the memory recall of the FCGs. We will provide a worksheet similar to Table 2 for all participants to help them track services and costs.

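### Caregivers come from three hospitals, but the primary slope comparison has no hospital term; adding one is a small, nearly free gain in precision and suits either way the lists may have been drawn.

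*Combined protocol and SAP*

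**What the plan says.** **Hospitals.** Under Setting: "The setting for this study is the Mayo Clinic Hospitals in Rochester and Mankato Minnesota and LaCrosse Wisconsin". The same section describes services of different size: "The Mayo Clinic Rochester service is organized into 3 teams", whereas the service at the other two hospitals "is smaller and includes one team for each site".

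**Control condition.** Under Control group: Usual care condition: "Control group care recipients will receive consult visits by the palliative care team while hospitalized, usual hospital discharge planning", followed by community care after discharge. The inpatient part of the comparator is therefore whatever the local hospital provides. The pre-discharge part of the intervention also works with the consult service and acute care staff.

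**Assignment.** Under Research Design: "FCGs will be randomly assigned to one of two groups by computer-generated randomization lists". No stratification, blocking or hospital factor is mentioned.

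**Primary analysis.** Under Analytical Plan, Aims 1 and 2, a least-squares slope in points per month is fitted for each caregiver: "This slope parameter estimate will be used as the response feature for each participant and is the primary endpoint for this study". The test is unadjusted: "The primary analysis of this endpoint will be analyzed using a two-sample t-test or Wilcoxon rank-sum test, as appropriate". An additional regression of the slope has "independent variables consisting of intervention (yes, no) as well as any baseline covariates such as" age and employment status. Hospital is not named.

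**Power.** Sample Size and Power Calculations gives 80% power for an effect size of 0.487 with 100 caregivers per group, two-sided alpha 0.01, with no hospital term. Neither expected enrolment by hospital nor between-hospital variance is given.

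**The concern.** Hospital is fixed before randomization and known for every caregiver. It also plausibly bears on the outcome, because the local team and discharge planning shape inpatient usual care and the setting of the pre-discharge visits. If caregivers' scores change at different rates at different hospitals, the unadjusted test counts that variation as noise.

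The consequence depends on a fact the documents do not give. If the lists ignore hospital, the arms can differ by chance in hospital mix and the primary test does not correct for it. If the lists are hospital-specific, that imbalance is largely removed, but the unadjusted standard error still includes the between-hospital variance and is therefore too large. In both cases precision is given up that a hospital term would recover.

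**Working it through.** **1. The plan's own figure.** With d = 0.487, SD 1, n = 100 per group and two-sided alpha 0.01, the noncentrality is 0.487 × sqrt(100/2) = 3.444 and the critical value of t on 198 df is 2.601. Power is 79.9% (80.7% by the normal approximation). The stated 80% is reproduced.

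**2. Plausible size of the hospital component (assumed).** Let p be the Rochester share and δ the difference in mean slope between Rochester and the other two hospitals, in within-hospital SDs. The share of slope variance explained is R² = p(1−p)δ² / [1 + p(1−p)δ²].

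| Rochester share | δ = 0.2 | δ = 0.3 | δ = 0.5 |
|---|---|---|---|
| one third | 0.009 | 0.020 | 0.053 |
| 0.6 | 0.010 | 0.021 | 0.057 |
| 0.8 | 0.006 | 0.014 | 0.039 |

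R² of 1-5% covers most of this range; 10% is shown as a generous case.

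**3. Power with hospital in the model.** The effect in residual SD units is 0.487/sqrt(1−R²). Residual df are 200 − 4 = 196.

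| R² | Standardized effect | Power | Detectable effect at 80% | Equivalent saving per arm |
|---|---|---|---|---|
| 0 | 0.487 | 79.9% | 0.487 | 0 |
| 0.01 | 0.489 | 80.4% | 0.485 | about 1 |
| 0.02 | 0.492 | 80.9% | 0.483 | about 2 |
| 0.05 | 0.500 | 82.3% | 0.475 | about 5 |
| 0.10 | 0.513 | 84.7% | 0.462 | about 10 |

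**4. Lists not split by hospital: chance imbalance.** The SD of the difference between arms in Rochester share is sqrt(2p(1−p)/100), which is 5.7-6.9 percentage points for the shares above. A gap over 10 points occurs in 8-15% of trials. At p = 0.6 and δ = 0.3, the 95% limit of the resulting shift is 1.96 × 0.0693 × 0.3 = 0.041 SD. At δ = 0.5 it is 0.068 SD. The standard error of the comparison is sqrt(2/100) = 0.141 SD.

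**5. Lists split by hospital: actual level.** The true variance of the difference is smaller by the factor 1−R², but the unadjusted test does not use this. Its level is about 2[1 − Φ(2.576/sqrt(1−R²))], which is 0.96% at R² = 0.01, 0.82% at 0.05 and 0.66% at 0.10.

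**6. Simulation.** Assumed hospital shares were 60/20/20, with 100 per arm, 20,000 null runs and 8,000 power runs per cell. Results at R² = 0.10:

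| Assignment | Test | Level (nominal 1%) | Power |
|---|---|---|---|
| not split | unadjusted t | 0.96% | 80.3% |
| not split | arm + hospital | 0.95% | 84.5% |
| split by hospital | unadjusted t | 0.69% | 81.5% |
| split by hospital | arm + hospital | 1.07% | 85.2% |

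Over R² from 0 to 0.10, the unadjusted t-test with lists not split ran at 0.96-1.11%, so it holds its level. The analysis term brings most of the gain. Stratifying as well adds 0.7 points, little more than the simulation error of about 0.4 points (one standard error) in each power figure.

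**The case against.** The case on the other side is substantial, and much of it stands.

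- **Pooled assignment is not established.** A reader might infer that all caregivers are drawn from one list. The documents are silent on this, and the plural in the assignment sentence is compatible with one list per hospital. Only the pooled analysis is explicit.
- **Validity is not at stake.** A reader might infer bias or an inflated error rate. Under assignment that ignores hospital, chance imbalance is part of the sampling error already in the standard error, and the shifts in step 4 are less than half a standard error even at their 95% limit. Under stratified lists the test errs on the cautious side.
- **The slope endpoint removes stable differences.** Hospitals that differ in baseline scores or case mix add nothing to the error unless caregivers' rates of change also differ. The documented contrast is mainly service size; nothing shows that the content of usual care differs.
- **Aim 3 is already modelled with adjustment.** The plan has Poisson regression accounting for baseline differences and multivariable-adjusted cost estimates. A reader might infer that every comparison in Aims 1-3 is unadjusted; that is not so. Hospital is simply not named.
- **Large gains need a large assumption.** A hospital difference of 0.8 SD would give a bigger effect, but it exceeds the 0.487 treatment effect and has no source in the documents.
- **Sample size.** The section also plans 500 caregivers per group. With 350 evaluable per group after 30% attrition, power at 0.487 is already above 99.9% and the gain vanishes. However, the plan's power case rests on 100 per group, and 8 per month for 36 months gives 288 in total, close to 2 × 100/0.70 = 286.

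The open covariate list does not fully answer the point. It belongs to an additional regression, not the primary test, and leaves the use of hospital to later discretion.

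**Conclusion.** The point holds as a modest, avoidable loss of precision in the primary test, together with an assignment description that does not say whether hospital is used. At 100 per group the gain from adjustment is about 0.5-2.4 power points if hospital explains 1-5% of slope variance, and about 5 points at 10%. These shares are assumptions; if hospitals do not differ in rate of change, the gain is nil and the loss negligible. The documents do not support a claim of bias, of an error rate above 1%, or of a need to redraw the lists. The change is worth making because it costs almost nothing and is right whichever way the lists were drawn.

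**What to change.** In Analytical Plan, Aims 1 and 2, make the primary comparison a linear model of the slope on arm plus hospital (three levels), combining Mankato and LaCrosse if either is very small. Where a rank test is preferred, use the hospital-stratified Wilcoxon (van Elteren) test in place of the rank-sum test. Name hospital as a covariate in the Aim 3 count and cost models. In Research Design, state whether the randomization lists are hospital-specific.

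The cost is two degrees of freedom out of 198 and a few sentences of wording, to be settled before outcomes are compared by arm. No new data are needed. Re-issuing lists is not required: in the simulation at R² = 0.10 it added only about 0.7 power points beyond the hospital term, and the documents do not say how many caregivers remain to be randomized.
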